6.2.1.1.3 Schedule A and B

Up to 12 treatment cycles can be administered to each subject as long as the subject is deriving benefit in the judgment of the investigator.

If the next higher dose is deemed reasonably safe by the DLRT, intra-subject dose escalation is allowed (see [Section 3.1](#)) and additional hospitalization and procedures are required (see [Section 7.2.2](#)).

Additionally, subjects will be hospitalized for a minimum of 72 hours under the following circumstances:

- after each dose step, if applicable
- after dose increase in case of intra-subject dose escalation

Subjects will be hospitalized for a minimum of 48 hours under the following circumstances:

- after re-start of treatment after an interruption due to adverse event

Approved

Subjects can be hospitalized for a longer time period at the discretion of the investigator. A nurse trained in emergency medicine or a physician must be available when the infusion of AMG 673 is started for immediate intervention in case of complications. The hospitalization period may be extended at the discretion of the investigator. During hospitalization periods, an immediately accessible emergency room with resuscitation equipment must be available.

Prior to hospital discharge, vital signs will be measured in order to detect possible signs and symptoms of cytokine release syndrome. If required for logistical reasons (eg, long travel times), subjects may be hospitalized the day before start of dosing (day -1) of any cycle for required PK samples.

The start time of infusion should be chosen carefully so as to avoid any interference or inconvenience with time points of safety assessments or PK/PD measurements. The site should record any unscheduled interruption of an infusion on the eCRF, and provide the start and stop date/time of the infusion.

AMG 673 should be administered through a central venous access at a constant flow rate. The drug should not be administered as a bolus. In the event that administration through a central venous access is not possible, AMG 673 may be administered through a peripheral venous line. The IPIM will have further information regarding drug preparation and administration for AMG 673.

The quantity administered, start date/time, stop date/time, and lot number of IP are to be recorded on each subject's eCRF.

6.2.1.2 Overdose

The effects of overdose of this product are not known. The administered AMG 673 dose may be up to 10% lower or higher than specified in the protocol. A dose of up to 10% higher than the intended dose may not require specific intervention.

In any case of overdose, consultation with the Amgen medical monitor is strongly recommended for prompt reporting of clinically apparent or laboratory adverse events possibly related to overdosage. Consultation with the Amgen medical monitor is also strongly recommended even if there are no adverse events, in order to discuss further management of the subject. If the overdose results in clinically apparent or symptomatic adverse events, the subject should be followed carefully until all signs of toxicity are resolved and the adverse event(s) should be recorded / reported per [Section 9.2.2.2](#).

A dose of >10% higher than the intended AMG 673 dose will be considered clinically important and classified as a serious adverse event under the criterion of “other medically important serious event” per [Section 9.2.2.2](#).

6.2.1.3 Dose-cohort Study Escalation and Stopping Rules, Dose Limiting Toxicities (DLTs)

A DLT will be defined as any of the events described below occurring in a subject during the DLT window, unless clearly attributable to causes other than AMG 673. The DLT window for Schedule A will start on D1 (start of the administration of the first infusion) and last for 14 days for cohorts receiving 2 doses (ie, day 1 and day 5 dose) and for 28 days for subjects receiving 4 doses (ie, days 1,5,12,19). The DLT window for Schedule B will start on D1 (start of the administration of the first infusion) and last for the duration of cycle 1 and 2 (ie, 28 days). The CTCAE (version 4) will be used to assess will be used to assess toxicities/adverse events with the exception of CRS (see [Table 5](#) for grading of CRS).

DLT Evaluation

A subject is not DLT-evaluable if he/she drops out before completion of the DLT window for reasons other than an AE. All available safety data for subjects who are not DLT evaluable will still be evaluated and considered in DLRM recommendations. A subject will be DLT-evaluable if the subject has received the minimum cycle 1 doses planned for the respective cohort defined below:

- Schedule A : 2 doses with a 14-day DLT window, or 4 doses with 28-day DLT window
- Schedule B: completed $\geq 70\%$ of the planned target doses (eg, 10 doses out of a 14-day cycle 1 for cohort 1, at least 9 doses of the 12 planned at target dose cohort 2, etc) with 28-day DLT window

Exception: If a subject has completed treatment as planned but drops out of study before completing the DLT window due to progressive disease, they will still be considered DLT-evaluable and will not be replaced. The DLT window may also be extended retrospectively to assess events starting or persisting outside the window in case the DLT definition is time dependent (eg, in case of neutropenia, see below).

Any adverse event occurring outside the DLT window that is determined by the investigator to be possibly related to the investigational product, which is seen more frequently or is more severe than expected or is persistent despite appropriate

management, can be determined to be a DLT upon unanimous decision by the DLRT after review of the adverse event and all available safety data.

Events to be considered as DLTs and exceptions are listed below:

- Any treatment-related death
- Grade 4 neutropenia persisting at 42 days after the last infusion in treatment cycle¹ in absence of evidence of active AML
- Grade 3–5 non-hematologic toxicity not clearly resulting from the underlying leukemia EXCEPT:
 - Alopecia
 - Grade 3 rash
 - Grade 3 fatigue, asthenia, fever, anorexia, or constipation
 - Grade 3 nausea, vomiting or diarrhea not requiring tube feeding, total parenteral nutrition, or requiring or prolonging hospitalization
 - Infection, bleeding, or other expected direct complication of cytopenias due to active underlying leukemia
 - Grade 3 infusion reaction, if successfully managed and resolves within 72 hours
 - Grade 3 tumor lysis syndrome if it is successfully managed clinically and resolves within 7 days without end-organ damage.
- Grade 3 or 4 isolated electrolyte lab abnormalities (ie, those occurring without clinical consequence) that resolve, with or without intervention, to < Grade 2 levels in < 72 hours will not be considered a DLT
- Grade 3 or 4 asymptomatic enzyme elevations including AST, ALT (without bilirubin elevation), GGT, lipase and amylase that resolve, with or without intervention, to ≤ Grade 2 within 7 days will not be considered a DLT.
- Grade 2 or 3 CRS meeting any of the criteria listed below:
 - Grade 2 CRS that does not resolve, with or without intervention to ≤ Grade 1 within 7 days will be considered a DLT
 - Grade 3 CRS that does not resolve, with or without intervention to ≤ Grade 2 within 5 days, or ≤ grade 1 within 7 days, will be considered a DLT
 - Grade 3 CRS reported at the initial dose (ie, at MTD₁; applicable only after MTD₁ has been defined) will be considered a DLT
 - Two separate grade 3 CRS events will be considered a DLT

Grade 4 CRS occurring during AMG 673 treatment.

See [section 6.2.1.3](#) and [6.2.1.4](#) for description of dose escalation and stopping rules and [section 3.4](#) for description of replacement of subjects.

Approved

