Dose Escalation will be conducted in 2 stages: a single subject stage (Schedule A only) and a multiple subjects stage. In the single subject cohorts, cohorts 1 and 2, single subjects will be enrolled at dose levels anticipated to be lower than those at which adverse events related to AMG 673 will be observed. Multiple subject cohorts, starting with cohort 3, will enroll and the cohort size will be extended to 3-4 subjects per cohort. The Bayesian logistic regression model (BLRM) design will be used to guide dose escalation. The actual dose selected at each dose decision may be at or below the model's recommended dose as determined by the dose level review team (DLRT) after considering all information. Subjects will be assessed for dose limiting toxicities (DLTs) for the duration of their first treatment cycle (ie, 2 weeks from D1 for subjects who receive 2 doses and 4 weeks for subjects who receive 4 doses in Schedule A and 4 weeks

from D1 for subjects in Schedule B). Subjects who complete the DLT period may proceed to a higher dose level for the following treatment cycle after the next dose level has been deemed safe by the DLRT, after consultation with Sponsor, if no DLT was reported for that subject and no \geq grade 3 adverse event(s), deemed treatment related by the investigator, are reported for that subject.

Estimation of initial and target MTDs

For Schedule A, it is anticipated that at least 2 MTDs may be estimated, one for the initial dosing and one for the subsequent step dosing. Should the initial dose be limited by adverse events related to first dose effects, the second MTD for the target dose will be estimated after giving the initial dose at MTD (step dose). Each MTD will be estimated following the dose escalation guided by BLRM described above. A second dose step may also be implemented in a cycle if this was considered appropriate and necessary to allow further dose escalation. This second dose step would be performed the same way as described above. In this case, a third MTD would be estimated for the dose to be administered after the second dose step.

Schedule B will be initiated after preliminary safety data of AMG 673 in Schedule A (eg, MTD1 is estimated to be $\geq 72 \mu\text{g}$) become available and may be conducted in parallel with Schedule A per Sponsor's decision. The MTD for Schedule B will be estimated following the dose escalation described in [Section 6.2.1.1.2](#) and guided by BLRM described above.

Expansion Cohort

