Schedule B will be initiated after preliminary safety data of AMG 673 in Schedule A (eg, MTD1 is estimated to be $\geq 72 \mu\text{g}$) become available and may be conducted in parallel with Schedule A per Sponsor's decision. For Schedule B, planned dose levels (dose per infusion) for the dose escalation cohorts are as follows: 72 μg , 110 μg , 160 μg , 240 μg , 360 μg , 480 μg and higher if MTD for Schedule B is not reached. The starting dose for the first cohort on Schedule B will be 72 μg administered as short-term IV infusions daily (QD) during the 14-day cycle 1. The doses administered for the subsequent cohorts will include step-up doses administered in increments of 2 days as described in [Table 4](#). The DLRT may recommend shortening the duration of steps to 1 day or to extend the duration of steps up to 5 days based on the emergent safety, PK and PD data. All subjects will be pre-treated with an 8-mg dose of IV dexamethasone 1 hour prior to the day 1 dose of AMG 673 and prior to each step-up dose of AMG 673 in cycle 1 and prior to all doses in subsequent cycles. Cycle 2 will start immediately after cycle 1 has completed and will consist of 4 AMG 673 infusions: day 1, day 4, day 8, and day 11 of a 14-day cycle at the target dose. Each cycle on Schedule B is planned for 14 days and intervals between cycles up to 2 weeks may be permitted after completion of cycle 2 upon discussion and agreement with Sponsor. Please refer to [Section 6.2.1.1.2](#) for additional information on Schedule B dose schedule, requirements and treatment-free intervals.

Estimation of MTDs

The estimate of the MTD or the estimate of each MTD if step dosing is used will use Bayesian logistic regression model (BLRM) design once a DLT is observed. DLTs experienced by subjects both during and after completing the DLT period will be considered in the BLRM design to account for any late onset toxicity. Schedule A may

result in 2 or more estimates of MTD; MTD1 without step dose, MTD2 with step dose and MTD3 with 2 step doses. Schedule B will utilize the step-up dose schedule described in [Section 6.2.1.1.2](#) to estimate MTD. A final estimate of the MTD and RP2D will be evaluated and confirmed utilizing all DLT evaluable subjects from the dose escalation and the dose expansion cohorts for each schedule.

MTD1 (Schedule A)

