In the expansion phase, all available study data will be reviewed (with recruitment ongoing) by the DLRT once the first 5 subjects have at least completed their first treatment cycle plus 2 weeks or dropped out of treatment / study, whichever occurs earlier. The MTD will be further evaluated by applying BLRM using all available data, including data from subjects in the expansion phase. Ad hoc meetings may be convened any time in case of important safety events (see also [section 10.3.2](#)).

A final estimate of the MTD and RP2D using BLRM will be evaluated and confirmed utilizing all DLT-evaluable subjects from the dose escalation and the dose expansion cohorts for each schedule. For definition of DLT-evaluable, see [section 6.2.1.3](#). Additional expansion cohorts testing alternative dose levels or biologic subsets may be considered by amendment.

The overall study design is described by a [study schema](#) at the end of the protocol synopsis section.

The study endpoints are defined in [Section 10.1.1](#)

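### Minor: a subject with unresolved grade 4 neutropenia who stops after cycle 1 leaves the study 7 to 14 days before the 42-day neutropenia DLT can be read

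*Protocol*

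**What the plan says.** **The criterion.** The DLT list in Protocol 6.2.1.3 includes "Grade 4 neutropenia persisting at 42 days after the last infusion in treatment cycle" followed by a raised 1, "in absence of evidence of active AML".

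**The window.** The synopsis (Dose Escalation Cohorts) says "Subjects will be assessed for dose limiting toxicities (DLTs) for the duration of their first treatment cycle". Section 6.2.1.3 sets the window, counted from day 1, at 14 days for two-dose Schedule A cohorts, 28 days for four-dose Schedule A cohorts and 28 days for Schedule B.

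**Late events.** For definitions that depend on time, 6.2.1.3 adds: "The DLT window may also be extended retrospectively to assess events starting or persisting outside the window", and gives neutropenia as its example. A persistent, possibly related event outside the window "can be determined to be a DLT upon unanimous decision by the DLRT". Protocol 3.1 says "DLTs experienced by subjects both during and after completing the DLT period will be considered in the BLRM design" and, for the end of the trial, "A final estimate of the MTD and RP2D using BLRM will be evaluated and confirmed utilizing all DLT-evaluable subjects" from escalation and expansion.

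**Leaving the study.** Protocol 3.5.1 and 7.2.4 put the end-of-study visit 4 weeks after the last dose, with up to one further week, or before other AML therapy if that starts sooner. A subject who has made that visit has completed the study.

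**Recording.** SAP section 5 takes a DLT from a yes answer on the Events eCRF, which the investigator decides under 6.2.1.3.

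**The concern.** One rule needs a neutrophil count 42 days after the last cycle 1 infusion. Another ends the subject's participation 28 to 35 days after the last dose. For a subject who receives only cycle 1, both clocks start at the same infusion, so the study ends before the DLT can be established.

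The criterion is aimed at subjects whose neutrophils stay very low although the leukaemia is not active. Protocol 2.3 anticipates neutropenia with this drug. A subject who leaves in that state after a completed window is DLT-evaluable. With no later count, nothing would prompt a yes on the eCRF, so the subject would presumably stand as a non-DLT in the model. That last step is an inference, because neither document says how such a subject is coded. At stake is complete ascertainment of one listed DLT in a first-in-human trial.

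**Working it through.** The plan gives no figure for this interval, so there is none to reproduce. The check is date arithmetic followed by a search for any other scheduled count.

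**1. Which cycle.** I read the raised 1 as cycle 1. The same list prints MTD1 with a lowered 1, and the synopsis ties DLT assessment to the first cycle. If the 1 is a footnote mark instead, the dates in step 2 are the earliest possible readings.

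**2. Dates.** Last cycle 1 infusion: day 5 or day 19 (Schedule A, 6.2.1.3) and day 14 (Schedule B, Table 3). Reading = last infusion + 42. Gap = reading − window close. End of study (EOS) after cycle 1 = last infusion + 28 to + 35.

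| Regimen | Last infusion | Reading | Window closes | Gap | EOS visit | EOS before reading |
|---|---|---|---|---|---|---|
| A, 2 doses | day 5 | 5 + 42 = day 47 | day 14 | 47 − 14 = 33 d | day 33–40 | 7–14 d |
| A, 4 doses | day 19 | 19 + 42 = day 61 | day 28 | 61 − 28 = 33 d | day 47–54 | 7–14 d |
| B | day 14 | 14 + 42 = day 56 | day 28 | 56 − 28 = 28 d | day 42–49 | 7–14 d |

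**3. Sensitivity.** The ±1 day dosing allowance makes the Schedule A gap 32 to 34 days. Counting the window to day 15 or 29 makes the gaps 27 to 32 days. Anchoring Schedule B to its last cycle 2 dose (day 25) gives 25 + 42 = 67 and a gap of 67 − 28 = 39 days. The EOS shortfall depends on none of this when the subject's last dose is the infusion that starts the 42 days: 42 − 35 = 7 and 42 − 28 = 14 days.

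**4. Is a later count scheduled elsewhere?**
- Protocol 7.2.2: weekly visits, but only in the interval between two cycles.
- Protocol 6.2.1.1.1 and 6.2.1.4: the interval may be extended for poor count recovery, up to 7 weeks, or 42 days for grade 4 neutropenia. Subjects held in this way are covered by the weekly visits.
- Footnotes to the Schedule A assessment tables: monitoring in an extended interval follows local practice, with no fixed day.
- Protocol 8.1: asks that subjects who stop treatment not be taken off study as a matter of course, but sets no date.
- Protocol 9.2.2.1: expects adverse events to be followed until they are stable or reversed, with no date. Stable grade 4 neutropenia could satisfy that. Appendix G also lists neutropenia among expected disease-related events.

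None of these gives a count 42 days after the last infusion to a subject who has stopped.

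**5. Who is left.** A subject with grade 4 neutropenia still present at EOS, no active AML, no other DLT, no new AML therapy, consent not withdrawn, treatment ended after cycle 1, and no interval extended for recovery.

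**6. Interim reviews.** With the minimum stagger in Protocol 3.1 (7 days, then 96 hours), three subjects start on calendar days 1, 8 and 12. The last window closes on calendar day 11 + 14 = 25 (A, 2 doses) or 11 + 28 = 39 (A, 4 doses; B). The first subject's reading is due on day 47, 61 or 56. At the earliest end-of-cohort review, nobody in the cohort can have been read for this criterion.

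**The case against.** The strongest reply is that the late reading is disclosed and provided for. Section 6.2.1.3 names neutropenia when it allows the window to be extended, and observed late DLTs reach later BLRM fits and the final MTD. The DLRT (Protocol 10.3.2) reviews post-window data and all toxicities of grade 3 or above, so it sees ongoing grade 4 neutropenia. It may delay dosing, may choose a dose below the model's (3.1), and may unanimously declare a persistent event a DLT. All of this stands. The 28 to 33 day gap is a design feature, and the absence of a formal pending status at interim is missing detail.

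A reader might infer from step 6 that the model is fed wrong data and escalates too fast. The documents do not support that: they do not state the interim coding, and the decision is not the model's alone. An illustration with an assumed prior shows only that coding could matter. It takes Schedule B with no DLTs at 72 µg and one pending subject among 3 or 4 at 110 µg. The prior uses the SAP 9.1 quantiles, with medians of 0.05 at 72 µg and 0.30 at the reference dose borrowed from SAP Appendix C. Reference doses of 160 to 480 µg and correlations of 0 or −0.5 are assumed. Counting the pending subject as a DLT changed the overdose rule (probability below 0.25) at 160 µg in 4 of 16 settings and left 12 unchanged. Switching any one subject moves so small a fit, so this is not specific to neutropenia.

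A reader might also infer that the criterion cannot be read at all. That goes too far: subjects held for recovery have weekly visits that span the 42 days. It is also fair that the unread group is very small and that 8.1 and 9.2.2.1 encourage follow-up. But encouragement without a date does not remove the conflict between the two rules.

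**Conclusion.** The point holds as a minor one. For a subject who stops after cycle 1 with unresolved grade 4 neutropenia, no active AML and no new AML therapy, the last scheduled count comes 7 to 14 days before a listed DLT can be established. The 28 to 33 day gap behind it rests on reading the raised 1 as cycle 1 and on nominal dosing days; the 7 to 14 day shortfall needs neither.

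It would be tempting to conclude that the MTD is biased. The documents give neither the frequency of such subjects nor the full prior, so the effect on the MTD cannot be determined. No sample size or precision statement in the plan changes.

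**What to change.** 1. In Protocol 6.2.1.3, change *may* to *will* in the sentence on retrospective extension of the window, for the grade 4 neutropenia criterion.
2. In Protocol 3.5.1 and 7.2.4, for a subject with grade 4 neutropenia and no active AML at the end-of-study visit, require local blood counts afterwards until recovery, new AML therapy or 42 days after the last infusion, whichever is first.
3. Optional: in Protocol 10.3.1 and 10.3.2 and SAP 7.1, flag such subjects as pending at each dose level review meeting and show the BLRM recommendation with them counted both ways, without holding escalation.

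The DLT definition and its starting point stay as they are. Items 1 and 2 cost amendment wording and about 1 to 2 weekly counts (7 to 14 days) in few subjects. Item 3 costs one extra model run at the meetings affected and may occasionally lead to a more cautious step.
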